6.2.3.2.2 Follow-Up COVID-19 Surveillance Visit

A Follow-Up COVID-19 Surveillance Visit will occur approximately 7 (+ 3) days after the Initial COVID-19 Surveillance Visit. This visit will consist of the following:

• Study staff will conduct the Follow-Up COVID-19 Surveillance Visit approximately 7 (+ 3) days after the Initial COVID-19 Surveillance Visit to ascertain worsening/ progression of COVID-19 symptoms. This follow-up visit by study staff will include all of the same procedures outlined in this section, including review of symptom history, measurement of vital signs (including pulse oximetry), and lung auscultation.

After the Follow-Up COVID-19 Surveillance Visit, participants will continue to receive telephone contacts approximately every week for ascertainment of COVID-19 symptom status until resolution of symptoms. Subsequent calls will document resolution or return to baseline of COVID-19 symptoms in order to calculate illness duration (date of symptom onset to day of symptom resolution) and will collect any additional healthcare visits, hospitalisations, and/or concomitant medications due to the suspected COVID-19.

Should a participant visit an emergency room, be admitted to the hospital or a COVID-19 ward, and PCR sampling is missed, then the local public health COVID-19 diagnostic test (or COVID-19 diagnostic test performed in the healthcare setting) will be taken as a valid result. Importantly, clinical data on symptoms, vital signs, exam findings, COVID-19 and other diagnostic testing, diagnoses, and complications occurring during the suspected COVID-19 emergency room and/or hospitalisation episode will be collected from available medical records on a study specific hospitalisation/emergency room data collection form in order to assess severity.

Participants will be notified of positive SARS-CoV-2 results as soon as locally practicable due to requirements of self-isolation and potential transmission.

Note that PCR-positive COVID-19 symptoms and events captured as efficacy endpoints will NOT be doubly recorded in the AE eCRF, unless a particular illness fulfils the definition of an SAE.

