2.2.2.2 Other Secondary Endpoints

- First occurrence of virologically confirmed (by PCR to SARS-CoV-2), symptomatic mild, moderate, or severe COVID-19, with onset at least 7 days after second study vaccination (e.g., Day 28) in adult participants regardless of their serostatus at baseline.
- First occurrence of COVID-19 requiring hospitalisation, intensive care unit (ICU) admission or mechanical ventilation linked to any virologically confirmed (by PCR to SARS-CoV-2) COVID-19 with onset at least 7 days after second study vaccination (e.g., Day 28) in adult participants regardless of their serostatus at baseline.
- First occurrence of virologically confirmed (by PCR to SARS-CoV-2), symptomatic mild COVID-19 (with no progression to moderate or severe COVID-19 during the course of the COVID-19 episode) with onset at least 7 days after second study vaccination (e.g., Day 28) in adult participants regardless of their serostatus at baseline.
- First occurrence of laboratory-confirmed (by PCR or nucleocapsid [N] protein serology to SARS-CoV-2) symptomatic or asymptomatic COVID-19 with onset at least 7 days after second study vaccination (e.g., Day 28) in adult participants regardless of their serostatus at baseline.
- Analysis of antibodies binding to the SARS-CoV-2 spike (S) protein by enzymelinked immunosorbent assay (ELISA) at Day 0 (baseline) and Day 35 (14 days after second study vaccination).
- The occurrence and relationship to study vaccination of SAEs and MAAEs related to study vaccination (in all adult participants) during the entire study period.
- The occurrence and relationship to study vaccination of AESIs and PIMMCs (in all adult participants) during the entire study period.
- The occurrence and severity of reactogenicity in terms of solicited local and systemic AEs (in all sub-study participants) for 7 days after each study vaccination.

• The occurrence, severity, and relationship to study vaccination of all MAAEs for 14 days after second vaccination and unsolicited AEs (in all adult participants) for 21 days after first study vaccination and 28 days after second study vaccination.

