6.1.5 COVID-19 Surveillance Visits (Unscheduled)

6.1.5.1 Initial COVID-19 Surveillance Visit

All participants will have the following procedures performed:

- Review of medical history, including prior and concomitant medical conditions, recent vaccinations (≤ 90 days), and significant surgical procedures.
- Prior and concomitant medications. Concomitant medications include all medications (including vaccines) taken by the participant.
- Vital sign measurements, including respiratory rate, blood pressure, pulse rate, pulse oximetry, and oral temperature (or via forehead/ear reader).
- Symptom-directed (targeted) physical examination, including a respiratory assessment.
- COVID-19 Symptom Diary. A participant with suspected or confirmed COVID-19 will be asked to complete the COVID-19 symptom diary. Participants should start the diary on their first day of symptoms and complete this diary daily for a minimum of 10 days even if their symptoms have resolved and regardless of any SARS-CoV-2 PCR results. They should continue the diary beyond 10 days if they have any ongoing symptoms related to the episode and should continue to do so until all symptoms have resolved.
- Assessment of MAAEs (related to study vaccination), SAEs, and AESIs.

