6.4 Safety Assessments

The timing and frequency of all safety assessments are listed in the SOE (Table 3-1).

After each study vaccination, including the licensed seasonal influenza vaccine for participants in the seasonal influenza vaccine co-administration sub-study, participants will remain under observation at the study site for at least 30 minutes for the presence of any acute reactions and solicited AEs. Solicited AEs, collected through an electronic diary (e-Diary), will be recorded at each study vaccination visit from the time of study vaccination until 7 days after study vaccination in all participants in the seasonal influenza vaccine co-administration sub-study and a subgroup of all other participants. Participants in the licensed seasonal influenza vaccine co-administration sub-study will record local reactogenicity for the study vaccine injection site only.

All participants will be assessed for unsolicited AEs from the time of first study vacation until Day 49; SAEs will be assessed from the time the informed consent is signed until completion of the participant's last study-related procedure; all MAAEs will be reported from the time of first study vaccination until Day 35; MAAEs related to study vaccination and AESIs will be reported from the time of first study vaccination until completion of the participant's last study-related procedure. All AEs will be followed until resolution or until clinically stable.

Safety assessments will include monitoring and recording of solicited (local and systemic reactogenicity events) and unsolicited AEs; MAAEs; AESI; SAEs; vital sign measurements on day of study vaccinations; and physical examination findings. COVID-19 severity will be categorised as virologically confirmed, mild, moderate, or severe according to protocol-specified criteria (Table 2-1). Recording of solicited and unsolicited AEs may be conducted by electronic data capture (EDC)/reporting. PIMMCs and AESIs specific to potential disease

enhancement for COVID-19 will also be monitored (see Section 9.5 [Appendix 4] for details).

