6.4.1.1.3 Adverse Events of Special Interest

Participants will be assessed for diagnosis of an AESI at all study visits. AESIs include PIMMCs, AEs specific to COVID-19, or other potential AEs that may be determined at any time by regulatory authorities as additional information concerning COVID-19 is obtained. Given the concern for cytokine storm, an AESI of cytokine release syndrome will be included as an AE specific to COVID-19. Listings of AESI are presented in Section 9.5, Appendix 4.

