6.4.1.3 Reporting Adverse Events

All AEs reported or observed during the study will be recorded on the AE page of the eCRF. Information to be collected includes study vaccine, type of event, time of onset, dosage, investigator-specified assessment of severity and relationship to study vaccine and/or study procedure, time of resolution of the event, seriousness, any required treatment or evaluations, and outcome. Any AEs resulting from concurrent illnesses, reactions to concurrent illnesses, reactions to concurrent medications, or progression of disease must also be reported. All AEs will be followed until they are resolved, stable, or judged by the investigator to be not clinically significant. The Medical Dictionary for Regulatory Activities (MedDRA) will be used to code all AEs.

Any medical condition that is present at the time that the participant is screened but does not deteriorate should not be reported as an AE. However, if it deteriorates at any time during the study, it should be recorded as an AE.

Any AE that is considered serious by the investigator or that meets SAE criteria (Section 6.4.1.1.1) must be reported to the sponsor within 24 hours after the investigator has confirmed the occurrence of the SAE. The investigator will provide a causality assessment (whether there is a reasonable possibility that the study vaccine caused the event) to the study vaccine. The sponsor will be responsible for notifying the relevant regulatory authorities of any SAE, in compliance with health authority requirements, as outlined in the relevant clinical study guidelines.

For this study, the following contact information will be used for SAE reporting:

Phone:	
Fax:	
Email:	

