Dermatologic	Chilblain-like lesions, single organ cutaneous vasculitis, erythema multiforme	

Abbreviations: AESI = adverse event of special interest; COVID-19 = coronavirus disease 2019; DAIDS = Division of AIDS; PCR = polymerase chain reaction; SARS-CoV2 = severe acute respiratory syndrome coronavirus 2.

^a To be recorded as AESIs relevant to COVID-19, these complications should be associated with a positive PCR test for SARS-CoV-2.

^b COVID-19 manifestations associated with more severe presentation and decompensation with consideration of enhanced disease potential (SPEAC 2020).

^c Cytokine release syndrome related to COVID-19 infection is a disorder characterised by nausea, headache, tachycardia, hypotension, rash, and/or shortness of breath (DAIDS 2017).

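### The rule against double recording in Section 6.2.3.2.2 excepts only SAEs, so it conflicts with AESI reporting for non-serious Table 9-4 conditions within efficacy-endpoint COVID-19 episodes

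*Protocol*

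**What the plan says.** The recording rule closes the section on the follow-up COVID-19 surveillance visit (Protocol 6.2.3.2.2): "Note that PCR-positive COVID-19 symptoms and events captured as efficacy endpoints will NOT be doubly recorded in the AE eCRF", with one exception, "unless a particular illness fulfils the definition of an SAE". AESIs are not mentioned there.

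Footnote a to Table 9-4 (Section 9.5) sets the entry condition for a COVID-19 AESI: "To be recorded as AESIs relevant to COVID-19, these complications should be associated with a positive PCR test for SARS-CoV-2".

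The AESI requirements elsewhere carry no seriousness condition:
- Section 6.4.1.1.3: "Participants will be assessed for diagnosis of an AESI at all study visits".
- Section 6.1.5.1, and in the same terms Section 6.1.5.2, list among the surveillance-visit procedures: "Assessment of MAAEs (related to study vaccination), SAEs, and AESIs". The schedule of events also marks AESIs in the surveillance column.
- Section 6.4: "MAAEs related to study vaccination and AESIs will be reported from the time of first study vaccination until completion" of the participant's last study procedure.
- Section 7.3.3 has AESIs through end of study listed separately and summarised by vaccine group.

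Section 6.4.1.3 names the place of record: "All AEs reported or observed during the study will be recorded on the AE page of the eCRF". The secondary safety endpoint in Section 2.2.2.2 is: "The occurrence and relationship to study vaccination of AESIs and PIMMCs (in all adult participants) during the entire study period".

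**The concern.** A COVID-19 AESI needs a positive PCR, and a positive PCR in a symptomatic participant inside the efficacy window is also what makes an efficacy case. A rule that keeps PCR-positive endpoint events off the AE page, and releases only SAEs, therefore meets the AESI definition head on. A site with a non-serious Table 9-4 condition in an endpoint case has one instruction to report it and another not to enter it in the only place the protocol describes for doing so.

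At stake is the completeness of a secondary safety endpoint. The matching objective in Section 2.1.2 covers AESIs relevant to COVID-19, including possible vaccine-enhanced disease, in all participants at any time after the first dose. If sites resolve the conflict differently, the AESI count depends on how each site reads one sentence.

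**Working it through.** No figure is involved, so the check sets the provisions side by side.

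**1. Scope of the rule.** Section 6.2.3.2.2 covers PCR-positive symptoms and events that are captured as efficacy endpoints. Section 6.2.2 limits efficacy endpoints to cases from 7 days after the second vaccination; one exploratory endpoint (Section 2.2.3) starts 14 days after the first. AESIs are collected from the first vaccination. PCR-positive complications before the efficacy window are therefore outside the rule and go on the AE page as usual.

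**2. Overlap on the narrow reading.** Suppose that only items named in the endpoint definitions count as captured. They still overlap with Table 9-4:

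| Endpoint item | Table 9-4 entry | Can it be non-serious? |
|---|---|---|
| Loss of taste or smell (Table 2-2) | Anosmia, ageusia | Yes |
| Deep vein thrombosis (Table 2-1, severe) | Deep vein thrombosis | If not admitted and not judged an important medical event |
| Hepatic dysfunction (Table 2-1, severe) | Liver injury | Same condition |

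For the last two rows, the outcome rests on the investigator's judgement under the important-medical-event clause of Section 6.4.1.1.1.

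**3. Overlap on the wide reading.** If events means the whole illness episode, the non-serious skin conditions in Table 9-4 (for example chilblain-like lesions) are caught as well, although they appear in neither Table 2-1 nor Table 2-2. The text does not settle which reading applies.

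**4. What is lost.** The endpoint asks for occurrence and relationship to vaccination. Relationship is collected on the AE page (Section 6.4.1.3, with the categories in Section 6.4.1.5). The efficacy capture described in Sections 6.2.3.2.1 and 6.2.3.2.2 consists of symptom history, vital signs, lung auscultation, healthcare contacts and medications, plus a hospital and emergency-room form used to grade severity. None of these is described as collecting causality, and no separate AESI form is mentioned. An event held only in the efficacy data therefore lacks one of the endpoint's two components, and it has no stated route into the summary planned in Section 7.3.3.

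**5. Consistency over time.** The same non-serious PCR-positive condition is entered as an AESI if it occurs before the efficacy window, but not if it occurs as part of an endpoint episode later. The endpoint is meant to cover the entire study period.

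**The case against.** The strongest reply is that the sentence only prevents duplication: the barred items are already in the efficacy record, and AESI assessment is expressly required at both surveillance visits. Much of this stands. Data on loss of smell are not lost as symptom data, and a deep vein thrombosis that meets Table 2-1 is counted as severe COVID-19. But the efficacy record as described carries no causality assessment and is not the stated source for the AESI summary. A requirement to assess does not say where to record when the AE page is closed.

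A second reply is that many Table 9-4 diagnoses, such as ARDS, stroke and pulmonary embolus, would usually be SAEs and so fall under the exception. That is right, and it confines the problem to conditions that can be non-serious.

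A third is that surveillance for enhanced disease does not rest on the AE page. Section 7.3.3.1 has the medical monitors review each confirmed case in real time, with SMC review, and Section 6.4.4 gives the SMC clinical event data for that purpose. This also stands. The weakness is in the AESI endpoint and its tabulation, not in all safety oversight.

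A reader might infer something stronger: that every non-serious COVID-19 AESI is unrecordable, or that the AESI count shrinks to SAEs. The documents do not support this. The rule is limited to what is captured as an efficacy endpoint. A positive PCR alone does not make a participant an efficacy case, and complications that are not themselves endpoint items are not clearly barred.

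**Conclusion.** The conflict is real but narrow. It concerns non-serious Table 9-4 conditions captured within an efficacy-endpoint COVID-19 episode: clearly anosmia and ageusia; deep vein thrombosis or liver injury when not judged serious; and skin lesions if the rule covers the whole episode. For these, following Section 6.2.3.2.2 as written leaves the by-arm AESI summary incomplete and omits the relationship assessment that the endpoint calls for.

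The size cannot be quantified. The protocol gives no frequency for non-serious Table 9-4 events among cases, and any count would rest on an invented rate. Efficacy endpoints and SAE reporting are unaffected.

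The conclusion assumes that the AE page is the only place where relationship to vaccine is collected for these events. That is all the protocol describes; a separate form or completion guideline, not available here, could narrow the gap in practice. The protocol's own sections would still need to be reconciled.

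**What to change.** Reconcile Section 6.2.3.2.2 with Sections 6.4 and 6.4.1.3 and with footnote a of Table 9-4. The simplest change is to extend the exception so that it applies when the illness or complication fulfils the definition of an SAE or of an AESI relevant to COVID-19 (Table 9-4). These events are then entered on the AE page with an AESI flag and relationship to vaccine, and feed the summary in Section 7.3.3. The exception need not extend to Table 9-3, whose conditions do not depend on a PCR result and are not COVID-19 endpoints.

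The cost is one phrase in the protocol, a note in the eCRF completion instructions, and some duplicate records, chiefly loss of taste or smell already held as a symptom. No endpoint definition or efficacy analysis changes.

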6.3 Immunogenicity Assessments

Blood will be collected from all participants for humoral immunogenicity according to the time points specified in the SOE (Table 3-1).

Immune measurements (ELISA) will be conducted on serum (IgG) for SARS-CoV-2 anti-S protein serology in approximately 900 participants in the Anti-S Protein Serology Subset and on anti-N protein serology in all participants. The immunologic test for SARS-CoV-2 serology based on a non-S protein (e.g., SARS-CoV-2 N protein) will be performed to identify cases of asymptomatic infection. Additional immunogenicity assessments specific to SARS-CoV-2 (or related variants) will include a neutralising antibody assay, which will be

SARS-CoV-2 rS Vaccine Novavax, Inc. Confidential Version 2.0 – 23 October 2020

performed in approximately 900 participants in a Neutralisation Assay Subset. Cell-mediated immune responses, as assessed by ELISpot \pm intracellular cytokine staining, will be performed in approximately 450 participants in the Cell-mediated Assay Subset. In addition, an HAI will be performed in the approximately 400 participants in the seasonal influenza vaccine co-administration sub-study.

Details on the handling, processing, and shipping of immunogenicity samples will be provided separately in a laboratory manual.

Participants will be asked to provide consent for the use of samples for future testing or assay development specific to SARS-CoV-2 (or related variants). Aliquots of all collected samples from this study may be retained for additional testing with antigens specific to SARS-CoV-2 (or related variants) for a maximum of 25 years (starting from the date at which the last participant had the last study visit), unless local rules, regulations, or guidelines require different timeframes or different procedures, in accord with participant consent.

6.4 Safety Assessments

The timing and frequency of all safety assessments are listed in the SOE (Table 3-1).

After each study vaccination, including the licensed seasonal influenza vaccine for participants in the seasonal influenza vaccine co-administration sub-study, participants will remain under observation at the study site for at least 30 minutes for the presence of any acute reactions and solicited AEs. Solicited AEs, collected through an electronic diary (e-Diary), will be recorded at each study vaccination visit from the time of study vaccination until 7 days after study vaccination in all participants in the seasonal influenza vaccine co-administration sub-study and a subgroup of all other participants. Participants in the licensed seasonal influenza vaccine co-administration sub-study will record local reactogenicity for the study vaccine injection site only.

All participants will be assessed for unsolicited AEs from the time of first study vacation until Day 49; SAEs will be assessed from the time the informed consent is signed until completion of the participant's last study-related procedure; all MAAEs will be reported from the time of first study vaccination until Day 35; MAAEs related to study vaccination and AESIs will be reported from the time of first study vaccination until completion of the participant's last study-related procedure. All AEs will be followed until resolution or until clinically stable.

Safety assessments will include monitoring and recording of solicited (local and systemic reactogenicity events) and unsolicited AEs; MAAEs; AESI; SAEs; vital sign measurements on day of study vaccinations; and physical examination findings. COVID-19 severity will be categorised as virologically confirmed, mild, moderate, or severe according to protocol-specified criteria (Table 2-1). Recording of solicited and unsolicited AEs may be conducted by electronic data capture (EDC)/reporting. PIMMCs and AESIs specific to potential disease

enhancement for COVID-19 will also be monitored (see Section 9.5 [Appendix 4] for details).

6.4.1 Adverse Events

AEs will be assessed during the study as described in the SOE (Table 3-1) and should be followed until they are resolved, stable, or judged by the investigator to be not clinically significant. AEs will be captured after the first dose of study vaccine administered with the exception of an AE related to study procedure or one that causes a delay in study vaccine administration (e.g., acute illness).

The investigator is responsible for ensuring that all AEs and SAEs are recorded in the eCRF and reported to the sponsor, regardless of their relationship to study vaccine or clinical significance. If there is any doubt as to whether a clinical observation is an AE, the event should be reported.

6.4.1.1 Adverse Event Definitions

The investigator is responsible for reporting all AEs that are observed or reported during the study, regardless of their relationship to study vaccination or their clinical significance.

An AE is defined as any untoward medical occurrence in a participant enrolled into this study regardless of its causal relationship to study vaccination. Participants will be instructed to contact the investigator at any time after randomisation if any symptoms develop.

